#### 6.2.4.4 Cardiac and Other Risk Factors

Cardiac and other risk factors will include the following:

- Any risk factor
- Ischemic coronary artery disease along with history of: angina pectoris; myocardial infarction; acute coronary syndrome; documented silent ischemia; percutaneous coronary intervention; history of stent placemen; coronary artery bypass surgery
- Other significant underlying cardiovascular (CV) disease (specify)
- Coronary artery vasospasm including Prinzmetal's angina
- Wolff-Parkinson-White syndrome or arrhythmias associated with other cardiac accessory conduction pathway disorders
- Other arrhythmias (specify)
- Stroke or transient ischemia attack
- Peripheral vascular disease
- Ischemic bowel disease
- Uncontrolled hypertension
- Triptan hypersensitivity (specify)
- Treated for hypertension
- Diabetes
- Current smoker
- Treated with statins
- Family history of coronary artery disease.

#### 6.2.4.5 Prior and Current Triptan Response

Prior triptan response will include historically discontinued triptan, route (e.g., intravenous, nasal), and reason for discontinuation (e.g., took too long to relieve headache pain) subcategorized as most or all of the time, some of the time, rarely, or never.

Current triptan response will include currently used triptan, route (e.g., intravenous, nasal), and durability of effect (e.g., freedom from pain within 2 hours, often satisfied with speed of pain relief) subcategorized as never, rarely, some of the time, most of the time, or all of the time.

# 6.2.4.6 Migraine Characteristics at On-Study Migraine Attack Onset

Characteristics at on-study migraine attack onset will include the following, and will be summarized only for mITT subjects:

- Pain level (none, mild, moderate, severe)
- MBS (nausea, phonophobia, photophobia)
- Nausea status (present, absent)
- Nausea level (none, mild, moderate, severe)
- Phonophobia status (present, absent)
- Phonophobia level (none, mild, moderate, severe)
- Photophobia status (present, absent)
- Photophobia level (none, mild, moderate, severe)
- Functional disability level (normal, mildly impaired, severely impaired, requires bedrest)
- Aura (yes, no).

See Section 7.6.3.2 for additional details.

An overall 3 x 3 cross-tabulation of the historical MBS (see Section 6.2.4.3) as rows, and the MBS at on-study migraine attack onset as columns will be presented for mITT subjects with non-missing paired MBS values. The number and percentage of subjects in the following row and column categories will be presented: nausea, phonophobia, photophobia, marginal total. In addition, the following statistics will be presented: asymmetric lambda value and 95% CI; symmetric lambda value and 95% CI; kappa coefficient value and 95% CI; and p-value from the chi-square test.

### 6.2.5 Exposure

#### 6.2.5.1 Study Medication

Subjects report study drug exposure in the eDiary, whereas sites report study drug accountability on the Study Drug Accountability CRF.

eDiary study drug exposure will be summarized by as-randomized treatment group, All BHV-3500, and overall for randomized subjects, and will include the number and percentage of subjects in the following categories:

- Study drug taken (i.e., study drug start date/time not missing)
  - o Study drug taken mistakenly before using eDiary (see Section 7.6.3.1)
  - Study drug actually received different from randomized treatment assignment (i.e., astreated treatment group not equal to as-randomized treatment group).

• Study drug not taken (i.e., study drug start date/time missing).

Study drug accountability will be summarized by as-randomized treatment group, All BHV-3500, and overall for randomized subjects, and will include the number and percentage of subjects in the following categories:

- Kit dispensed and returned
  - Investigational product (IP) used
  - o IP not used
  - o IP use unknown or not reported (i.e., missing)
- Kit dispensed and not returned.

Two 2 x 2 cross-tabulations of eDiary study drug exposure and study drug accountability will be provided for randomized subjects by overall only. The number and percentage of subjects in each category will be summarized follows:

- Categories for study drug exposure in rows are "study drug taken" and "study drug not taken". Categories for study drug accountability in columns are "kit dispensed and returned" and "kit dispensed and not returned".
- Categories for study drug exposure in rows are "study drug taken" and "study drug not taken". Categories for study drug accountability in columns are "IP used" and "IP not used/unknown/not reported".

A by-subject listing of eDiary study drug exposure and study drug accountability will be provided for randomized subjects. Subjects for whom the eDiary study drug exposure and study drug accountability categories (as per cross-tabulations) do not match will be flagged.

# 6.2.5.2 Non-Study Medications

Non-study medications will be summarized by therapeutic class and preferred name in descending order of overall frequency. For each subject, multiple records of the same medication will be counted only once within each therapeutic class and preferred name. Imputed medication start and stop dates will be used to assign non-study medication type (prior or concomitant) to all non-study medications except rescue medications. See Section 7.6.2 for details on non-study medication start and stop date imputation, and definitions of non-study medication types.

The following non-study medications will be summarized by as-treated treatment group and All BHV-3500 for treated subjects:

- Prior medications, including results for overall treatment group: all; prophylactic migraine
- Current medications, including results for overall treatment group: all; prophylactic migraine
- Concomitant medications: all; prophylactic migraine
- Rescue medications.

Rescue medications will also be summarized by as-randomized treatment group for mITT subjects to support efficacy.

A by-subject listing of non-study medications will be provided by therapeutic class and preferred name for enrolled subjects. Prophylactic migraine and rescue medications will be identified, as well as medication type.

A by-subject listing of rescue medications will be provided by therapeutic class and preferred name for treated subjects.

Non-study medications will be identified from the Concomitant Medication and Rescue Medication CRFs.

Prophylactic migraine medications are defined as those with a "yes" response to the question about prophylactic migraine medication on the Concomitant Medication CRF.

Rescue medications are defined as non-study medications reported on the Rescue Medication CRF with complete medication dates, and either (1) medication date/time after the study drug start date/time, or (2) medication date at or after study drug start date if the medication time or study drug start time is missing. Rescue medication dates will not be imputed. Rescue medication times will not be imputed, unless specified otherwise (see Section 6.3.5.2).

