4.2 Study Schematic

4.3 Schedule of Assessments

Table 1: Schedule of Assessments

Procedure	Screening Visit ¹	Baseline/ Randomization Visit (Day 1) ²	Onset of moderate or severe migraine ³	Post Study Medication Administration: 15, 30, 45, 60 and 90 minutes 2, 3, 4, 6, 8, 24 and 48 hours	End of Treatment Visit ¹⁴
		Elig	ibility Assessments		
Informed Consent	X				
Inclusion/ Exclusion Criteria	X	X			
Medical History	X				
Migraine History Assessment (signs/ symptoms/ prior treatment/ frequency/ intensity)	X				
Rescue Medication paper diary, Concomitant Medication paper diary ⁴	X	X	X	X	X
Randomize subject in IWRS ⁵		X			
		Sa	fety Assessments		
Physical Examination	X				X
Nasal Inspection ⁶	X	X			X
Vital Signs/ Physical Measurements ⁷	X	X			X
Adverse Event and Serious Adverse Event Assessment ⁸	X	X	X	X	X
Sheehan Suicidality Tracking Scale (S-STS) ⁹	X	X			X
ECG	X				X
Clinical Safety Laboratory Testing	X				X

		Baseline/ Randomization Visit	Onset of moderate or	Post Study Medication Administration: 15, 30, 45, 60 and 90 minutes	End of Treatment
Procedure	Screening Visit ¹	$(Day 1)^2$	severe migraine ³	2, 3, 4, 6, 8, 24 and 48 hours	Visit ¹⁴
Liver Function Tests (LFTs)					X
Lipid Panel	X				
FSH, if applicable, to determine WOCBP status	X				
Pregnancy Test ¹⁰	X (Serum)	X (Urine)	X (Urine)		X (Serum)
Urinalysis	X				X
Urine drug screen for drugs of abuse	X				X
		Clinical Dru	ig Supplies/Study Supplie	s	
eCOA Handheld device assigned		X			
Dispense study medication ¹¹		X			
Administer study medication			X		
Patient Education: Dose Administration		X			
Patient Education: eCOA Handheld		X			
Enter use of study medication in eCOA Handheld device			X		
Return used or unused study medication					X
eCOA Handheld returned/ reviewed for completeness ¹²					X

Procedure	Screening Visit ¹	Baseline/ Randomization Visit (Day 1) ²	Onset of moderate or severe migraine ³	Post Study Medication Administration: 15, 30, 45, 60 and 90 minutes 2, 3, 4, 6, 8, 24 and 48 hours	End of Treatment Visit ¹⁴
Efficacy Assessments ¹²					
Assessment of migraine pain ¹³			X	X	
Assessment of Migraine Symptoms (photophobia, phonophobia, and nausea) ¹³			X	X	
Functional Disability Scale ¹³			X	X	
MQoL (Migraine Quality of Life Questionnaire) ¹³				X (24-hour assessment)	
Preference of Medication (PoM) ¹³				X (24-hour assessment)	

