5.4.1 Rescue Medications

After dosing with study medication, all other headache medication is prohibited during the first 2 hours post dose of study drug administration. A subject who does not experience relief of their migraine headache at the end of 2 hours after dosing with study medication (and after the two hour assessments have been completed on the handheld device), will be permitted to use ONLY the following rescue medication: aspirin, ibuprofen, acetaminophen up to 1000mg/day (this includes Excedrin Migraine) Naprosyn (or any other type of non- steroidal anti-inflammatory (NSAID)), antiemetics (e.g., metoclopramide or promethazine), or baclofen. These are the only medications allowed for rescue treatment after 2 hours post dose of study medication.

If the migraine is relieved by study medication at 2 hours after dosing but then returns to a moderate or severe intensity level between 2 and 48 hours, the subject will be permitted to take the same rescue therapy as outlined above.

If needed, 48-hours after dosing with the study medication (and before returning to the clinical site for the End of Treatment Visit), the subject may take their prescribed standard of care medications for treatment of migraine (including triptans if not contraindicated), provided all of the assessments have been completed on the handheld.

In all circumstances, the subject will always continue to complete the handheld entries through the 48-hour assessment after taking the study medication. Use of concomitant medication after randomization, including rescue medication, will be recorded by the subject on a paper diary and returned to the site. The site will record medications that were taken within 14 days of dosing with study medication (or until the End of Treatment Visit) in the EDC.

During the 45 days of the treatment phase, if the subject has a nonqualifying migraine (mild migraine) or a migraine that they do not treat with study medication, the subject is permitted to use only the following medications: aspirin, ibuprofen, Naprosyn (or any other type of non-steroidal anti-inflammatory (NSAID)), antiemetics (e.g., metoclopramide or promethazine), or baclofen.

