# 6.3.1 Principal Analysis Methods of Handling Missing Data and Intercurrent Events

Methods of handling missing data in principal analyses of binary efficacy endpoints are defined as follows:

- Non-Completer = Failure (NC=F): Subjects with missing data at a single time point will be classified as failures. This missing data imputation method will be applied to endpoints based on data from a single time point (e.g., co-primary endpoints at 2 hours post-dose).
- Non-Completer With Missing Data at More Than 1 Time Point = Failure (NC1=F): Subjects with missing data at > 1 time point post-dose in a specified time period will be classified as failures. This missing data imputation method will be applied to endpoints that are based on data from multiple time points (e.g., secondary endpoint of sustained pain freedom from 2 to 24 hours post-dose).
- Non-Completer = Missing (NC=M): Subjects with missing data at a single time point will be excluded from the analysis. This missing data exclusion method will be applied to endpoints based on data from a single time point (e.g., co-primary endpoints at 2 hours post-dose).

The intercurrent event of rescue medication use will be handled using Rescue Medication = Failure (RM=F), i.e., subjects who take rescue medication will be classified as failures for all efficacy evaluations that are reported at or after taking rescue medication, i.e., (1) rescue medication start date/time  $\leq$  eDiary finding date/time if start time is not missing, or (2) rescue medication start date  $\leq$  eDiary finding date if start time is missing; see Sections 6.2.5.2 and 7.3). This method will apply to all efficacy analyses, except the secondary endpoint of rescue medication use within 24 hours post-dose.

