## 7.3 Derived Dates

Derived dates are defined as follows:

- Study drug start date/time: Earliest study medication date and time from the eDiary Migraine Report or Study Medication Intake Report (see Section 7.6.3.1). This date is used to define analysis periods.
  - o eDiary Migraine Report
    - If the subject answered "yes" to taking study medication mistakenly already, then the following conventions will be applied depending when drug was reported taken:
      - Today: study drug start date will be set to the finding date, and the study drug start time will be set to the time of study medication taken, if available.
      - Yesterday: study drug start date will be set to the finding date -1 day, and study drug start time will be set to the time of study medication taken, if available.
      - Other: study drug start date will be set to the date of study medication taken, if available.
    - Otherwise, if the subject answered "no" to taking study medication mistakenly already and answered "yes" to confirming having taken study medication, then the study drug start date/time will be set to the finding date/time.
  - o Study Medication Intake Report: Study medication date/time.
- Rescue medication start date/time: Earliest rescue medication date/time (see Section 6.2.5.2). Missing time is considered to be earlier than non-missing time on the same date.
- Imputed rescue medication start date/time: This will be used only for time-to-event efficacy analyses in Section 6.3.5.2, and not for time to rescue medication use analyses in Section 6.3.4.3.
  - o If the rescue medication start date and time are both not missing, then the imputed rescue medication start date/time will be set to the rescue medication start date/time.
  - If the rescue medication start time is missing and the rescue medication start date is
    equal to the study drug start date, then the imputed rescue medication start date/time will
    be set to the study drug start date/time.
  - Otherwise, if the rescue medication start time is missing and the rescue medication start date is equal to a post-dose eDiary finding date with non-missing efficacy data, then the imputed rescue medication start date/time will be set to the first eDiary finding date/time corresponding to non-missing efficacy data.
  - Otherwise, if the rescue medication start time is missing and rescue medication start date is equal to the study drug start date + 1 day, then the imputed rescue medication start

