date/time will be set to the study drug start date/time + upper bound of the *X*-hour analysis window (see Table 5).

• Last contact date: (1) Complete death date, if it exists; (2) otherwise, the maximum complete date of the following: AE start/stop; ECG; eDiary finding; eDiary study drug start; informed consent; IWRS randomization; laboratory collection; non-study medication start/stop; physical measurement; procedure; rating scale; questionnaire; study completion/discontinuation from Study Exit Status CRF; vital sign; visit.

No date imputations are performed on these derived dates. Complete dates are those with valid, non-missing day, month, and year.

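### A rescue record with an incomplete date drops out of the analysis, so a recorded rescue user can be scored as a responder, a non-relapser or a 24-hour non-user

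*SAP*

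**What the plan says.** **Estimand.** SAP 2.3 handles rescue medication taken at or before the time point of interest with a composite strategy. SAP 6.3.1 makes this operational as RM=F: "subjects who take rescue medication will be classified as failures for all efficacy evaluations" reported at or after the rescue.

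**What counts as rescue.** SAP 6.2.5.2: "Rescue medications are defined as non-study medications reported on the Rescue Medication CRF with complete medication dates", timed after study drug. The same section adds: "Rescue medication dates will not be imputed". SAP 7.3 takes the rescue start as the earliest record meeting that definition and says of its derived dates: "No date imputations are performed on these derived dates".

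**What a missing rescue start means.** The responder rules for pain freedom (6.3.3.1), MBS freedom (6.3.3.2) and sustained pain relief (6.3.4.5, 6.3.4.6) treat a missing rescue start date/time as meeting the no-rescue condition. Sustained pain freedom (6.3.4.7, 6.3.4.8) and the non-relapser rule (6.3.4.9) adopt this by cross-reference.

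**Missing time.** Under 6.3.1, a complete rescue date without a time gives failure for evaluations on or after that date. In 6.3.4.3, a subject with such a record dated no later than the day after dosing is excluded from the 24-hour rescue endpoint.

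**Data capture.** Protocol Table 1 lists "Rescue Medication paper diary, Concomitant Medication paper diary" as the source. Sites review the returned diaries and enter them in the EDC.

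**The concern.** The SAP treats the poorer record more favourably than the better one. A subject who wrote down a rescue drug and its date but no time is failed. A subject who wrote down the drug with only a month, or no date, has no rescue medication at all under 6.2.5.2. If that subject's diary shows no pain, the result is a response.

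The same derived variable feeds both co-primary endpoints, the sustained endpoints, relapse and the 24-hour rescue endpoint. The estimand says that rescue is failure, and these subjects would break that rule although their rescue use is in the database. Paper diaries transcribed later make some incomplete dates foreseeable.

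**Working it through.** **1. Following one record through the rules.** Suppose a subject's only rescue entry is an NSAID with month and year but no day.

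| Step | SAP section | Complete date, no time | Incomplete date |
|---|---|---|---|
| Is it rescue medication? | 6.2.5.2 | Yes, if on or after the dosing date | No |
| Derived rescue start | 7.3 | Date only | Missing |
| Single-time-point and sustained endpoints | 6.3.1, 6.3.3, 6.3.4 | Failure for evaluations on or after that date | No rescue; diary decides |
| Relapse, 2 to 48 hours | 6.3.4.9 | Relapser if rescue falls in the window | Non-relapser if diary qualifies |
| Rescue within 24 hours | 6.3.4.3 | Excluded if dated by the day after dosing | Counted as non-user |

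**2. Does another rule catch it?**
- The imputed rescue start in 7.3 needs a rescue date in every branch and is used only for the time-to-event analyses in 6.3.5.2.
- SAP 7.6.2.1 and 7.6.2.2 contain a partial-date algorithm for non-study medications, but 6.2.5.2 exempts rescue medications from it.
- The sensitivity analyses in 6.3.3.1, 6.3.3.2 and 6.3.5.2 vary the handling of missing diary data. Each applies the same RM=F rule before doing so, so none tests the rescue definition.
- Concomitant-medication deviations (6.2.3) are summarised and listed, with no effect on responder status.

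**3. The plan's own power.** Inputs from SAP section 5: n = 380 per arm, alpha = 0.0167, pain freedom 22% vs 12%, MBS freedom 45% vs 32%. Sidedness is not stated there; I take it as two-sided, so z = 2.393.

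Power = Φ[(|p1 − p2| − z·s0) / s1], with s0 = √(2·p̄(1 − p̄)/n) and s1 = √(p1(1 − p1)/n + p2(1 − p2)/n).

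- Pain freedom: s0 = 0.02725, s1 = 0.02701; (0.10 − 2.393 × 0.02725)/0.02701 = 1.288; power 90.1%.
- MBS freedom: s0 = 0.03530, s1 = 0.03498; (0.13 − 2.393 × 0.03530)/0.03498 = 1.301; power 90.3%.
- Product: 0.901 × 0.903 = 0.814, the plan's roughly 80%.

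The stated power reproduces. The problem is in the definition and not in this calculation.

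**4. Illustration of size.** The documents give no rate of incomplete rescue dates, so the rates below are assumptions. They are percentage points of the mITT arm that a stricter rule would move from responder to failure for pain freedom at 2 hours, starting from 22% vs 12%.

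| Moved, active / placebo (points) | Subjects, active / placebo | Rates | Difference | Power |
|---|---|---|---|---|
| 0 / 0 | 0 / 0 | 22 vs 12% | 10 | 90.1% |
| 0.25 / 0.25 | about 1 / 1 | 21.75 vs 11.75% | 10 | 90.5% |
| 1 / 1 | about 4 / 4 | 21 vs 11% | 10 | 91.6% |
| 2 / 2 | about 8 / 8 | 20 vs 10% | 10 | 93.1% |
| 1 / 0 | about 4 / 0 | 21 vs 12% | 9 | 83.0% |
| 2 / 0 | about 8 / 0 | 20 vs 12% | 8 | 73.2% |
| 0 / 1 | 0 / about 4 | 22 vs 11% | 11 | 95.6% |
| 0 / 2 | 0 / about 8 | 22 vs 10% | 12 | 98.4% |

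Equal misclassification leaves the difference at 10 points and changes power little. An imbalance moves the difference point for point, in whichever direction the imbalance runs.

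**The case against.** **The event may be rare.** Diaries come back at a visit due within 7 (+2) days of dosing, so a site can query a missing day soon after use. An incomplete date matters only when the subject has no other qualifying rescue record in the window. At 2 hours the exposure should be small, because Protocol 5.4.1 says "all other headache medication is prohibited during the first 2 hours post dose of study drug administration" and allows listed rescue only after the 2-hour assessment. All of this stands and limits the likely size, but it does not change the rule. The 24- and 48-hour endpoints cover the period when rescue is permitted.

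**A reader might infer that headache drugs on the Concomitant Medication CRF escape the rule and that this contradicts the estimand.** The SAP does say "Non-study medications will be identified from the Concomitant Medication and Rescue Medication CRFs", and RM=F reads only the second of these. But 6.2.5.2 does not confine rescue to the protocol's permitted list or to use after 2 hours, so a prohibited or early drug entered on the Rescue Medication CRF counts. No passage sends such drugs to the other form. SAP 2.3 also names only rescue medication as the intercurrent event. Reading the second form would widen the definition; that is a reasonable sensitivity analysis and not the repair of a contradiction.

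**A reader might infer that the rule favours the drug.** It favours the individual subject's score in any arm, placebo included. If placebo subjects have more incompletely dated rescue, the rule works against BHV-3500.

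**Conclusion.** The incomplete-date gap holds on the text. Sections 6.2.5.2 and 7.3, read with the responder rules, allow a recorded rescue user to be scored a responder, a non-relapser or a 24-hour non-user, contrary to the composite strategy and out of line with the treatment of a missing time. No planned sensitivity analysis would show it.

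Its size cannot be computed from the documents. It depends on how many subjects have an incompletely dated record as their only rescue record in the window, and on how they split between arms. The figures above assume rates for pain freedom at 2 hours; nothing comparable can be calculated for the 24- and 48-hour endpoints, where exposure is probably larger, because the plan gives no response rates for them. The documents support neither a claim of bias toward BHV-3500 nor a claim that the choice of CRF breaches the estimand.

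**What to change.** 1. In SAP 6.2.5.2 and 7.3, add a rule for use after date queries are exhausted. A Rescue Medication CRF record whose incomplete date is compatible with the interval from study drug start to the end of the endpoint window counts as rescue taken, hence failure under RM=F (relapser in 6.3.4.9).
2. On the 24-hour rescue endpoint, handle such a record consistently with the missing-time rule in 6.3.4.3.
3. Report the affected endpoints with and without this rule.
4. For the co-primary and sustained endpoints, add a sensitivity analysis that also counts as rescue any post-dose drug on the Concomitant Medication CRF judged, in blinded review before lock, to have been taken for headache or migraine symptoms. Judge by indication and not by drug class alone. Exclude stable prophylaxis, low-dose cardiovascular aspirin (which Protocol 5.4 permits) and drugs for unrelated indications.

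**Cost.** SAP wording, date queries and a small blinded review of data already collected. Response rates may fall slightly. Some records with only month or year known will be failed although the drug was taken after the window, including for the 2-hour endpoints; this is why both versions should be shown.
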